10.0 VACCINATION OF PATIENTS WITH ADXS11-001

Two vaccinations with ADXS11-001 will be given at a dose of 1×10^9 cfu intravenously according to the schedule described in the **Study Calendar** above. The drug will be given by a 500ml infusion over 60 minutes through a separate and distinct infusion line with each infusion and this line is to be used for prophylactic medication, pre-medication and ADXS11-001 administration. The line is to be removed prior to patient leaving the clinic and a new line is to be placed with each administration. For safety monitoring purposes, enrollment of the first 3 subjects at any site will be staggered by at least 2 weeks. Once any site has enrolled 3 subjects, then all sites can enroll subjects concurrently.

ADXS11-001 **must not be administered** via an existing or newly placed central venous catheter or infusion port which is planned to be used for another purpose. In addition, the central venous catheter or infusion port **must not be used** for a minimum of 72 hours following the completion of the ADXS11-001 infusion AND following the subject's first dose of oral antibiotics.

- 10.1 Pre-treatment prophylactic medication regimen: Mild to moderate cytokine release symptoms (e.g., constitutional symptoms such as fever, chills, rigors, fatigue, headache, nausea, vomiting, tachycardia, shortness of breath, hypotension and rash) are commonly

seen and typically occur 2-4 hours after ADXS11-001 infusion and often resolve within 12-24 hours. Prophylactic medications are intended to reduce the inflammatory response. Subjects should receive the following pretreatment prophylaxis regimen.

IV Fluid Hydration:

- Normal saline (e.g., 500 mL over approximately 30-60 minutes)

Premedication Regimen:

- Antihistamine – PO or IV (e.g. diphenhydramine 25 mg or equivalent), once
- NSAIDs - PO (e.g., naproxen 220 mg or ibuprofen, 400 mg), once
- Antiemetic - PO or IV (e.g., promethazine or ondansetron), once
- Histamine H2-receptor antagonist – PO or IV (e.g., famotidine 20 mg or equivalent)

Pretreatment medication should be given on the day of dosing and completed at least 30 minutes prior to the start of the assigned study treatment. Additional NSAID doses and antiemetic administration should be given per label or package insert post initial administration on Day 1 and Day 2 of the ADXS11-001 infusion, as needed. The prescribed dosage of the selected NSAID and antiemetic will be at the discretion of the Investigator.

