- 10.6 Subjects will receive a 6 month course of oral trimethoprim/sulfamethoxazole or ampicillin for subjects with sulfa allergies to be initiated approximately 72 hours of resuming oral intake after transoral surgery, or at the time of study discontinuation. For those patients for whom resumption of oral intake is delayed beyond 72 hours, an alternative delivery route (e.g. gastrostomy tube) may be employed. Trimethoprim/sulfamethoxazole therapy should consist of either 160 mg trimethoprim/800 mg sulfamethoxazole (DS) tablet administered three times a week or 80 mg trimethoprim/400 mg sulfamethoxazole administered daily for 6 months. The dose of ampicillin consists of 500 mg four times daily for 6 months. Review the approved product labeling for Bactrim and ampicillin, and monitor antibiotic tolerance as dosing adjustments may be necessary.
- 10.7 Lm Surveillance Monitoring: In addition, all subjects will participate in a three-year Lm surveillance period. Surveillance monitoring for the detection of Lm will be initiated at the completion of study treatment according to the protocol or at the time of study discontinuation if earlier. This surveillance monitoring period will consist of a 6-month course of oral antibiotics, obtaining a blood sample to monitor CBC, CMP, including CRP and ESR, and blood cultures at regular intervals. This testing will be performed on all subjects who have received at least 1 dose of ADXS11-001. It will occur at 3 months (± 2 weeks), 6 months (± 3 weeks), 9 months (± 1 Month), 12 months (± 1 Month), and every 4 months (± 1 Month) for year 2 and year 3 postoperatively. If a persistent increase in CRP and/or ESR is observed with negative blood cultures for *Listeria* during this time, the subject should be evaluated and treated, as appropriate, for another possible cause. In the event that a definite cause has not been identified, subjects must continue to be monitored closely, including additional testing and a blood culture, for possible signs/symptoms of listeriosis. This testing may be performed at the investigational site or at another acceptable location following consultation with the study chair.
- 10.8 **Treatment modification:** The dose of ADXS11-001 will not be modified (i.e., reduced or increased). However, treatment may be delayed or discontinued based on toxicities, as shown below in Table A.

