Treatment modification and supportive care guidelines for cytokine release are included in Appendix A and for infusion related toxicities are included in Appendix B.

Table A: Treatment Delay/Discontinuation Guidelines for Drug-Related Adverse Events

Toxicity	Grade	Result	Action
Hematologic and non-hematologic, excluding cytokine release symptoms	1-2		Continue therapy
	3	Toxicity resolves to \leq Grade 1 or baseline within 2 weeks of last infusion	Restart therapy
	3	Toxicity not resolved to \leq Grade 1 or baseline within 2 weeks of last infusion	Discussion with study chair required
	4		Permanent discontinuation from Study

In case toxicity does not resolve to Grade 0-1 within 2 weeks after the last infusion, trial treatment should be discontinued after consultation with the Sponsor. With Investigator and Sponsor agreement, subjects with a laboratory AE still at Grade 2 after 2 weeks may continue treatment in the trial only if asymptomatic and controlled. For information on the management of AEs, see Section 4.6 (Supportive Care).

10.9 MAJOR AND MINOR SURGERIES AND ADXS11-001 TREATMENT: No formal studies of the effect of ADXS11-001 on wound healing have been conducted. However, based on its mechanism of action it is not expected that administration of ADXS11-001 would complicate wound healing. Therefore, a subject may initiate or resume study treatment 2 weeks after minor surgery (i.e., surgery involving little risk to the life of the subject; specifically an operation on the superficial structures of the body or a manipulative procedure that does not involve a serious risk) if the wound has completely healed and there are no wound healing complications. A subject who has wound healing complications following minor surgery, received major surgery or requires new implants and/or devices (permitted by the protocol) during the course of the study, must wait a minimum of 6 weeks and must have recovered from any toxicity (e.g., return to baseline or Grade 1) and/or complication before the next infusion of study treatment. Sponsor consultation is required prior to resuming study treatment for these subjects. If the treatment is delayed due to concomitant surgery beyond 12 weeks, the subject may be discontinued from the study.

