12.0 SCHEDULE OF BLOOD AND SAMPLE COLLECTION

12.1 TREATMENT GROUP

1. The day of the first dose of vaccination will be considered “day 1”.
2. Standard-of-care pre-treatment tumor biopsy will be performed in a timely fashion for those patients without a prior biopsy, whose prior biopsy is inadequate for clinical planning, or for whom prior biopsy material adequate for immunophenotyping by immunohistochemistry (IHC) is not available.
3. Initial blood draw (Draw 1) will be obtained prior to the first vaccination usually during screening visit.
4. Draw #2 will be performed on the day of the first vaccination (e.g. day 1) before vaccine infusion.
5. Draw #3 will be performed on the day of the second vaccination (day 15) before vaccine infusion.
6. Surgery, and harvest of tumor and TIL, will be performed on day 35 +/- 7 days following entry into the study and baseline blood draw.
7. Draw #4 will be performed preoperatively, on the day of surgery prior to induction of anesthesia, or up to 72 hours prior to the surgery.
8. Draw #5 will be performed 3 weeks (+/- 1 week) after surgery.
9. Draw #6 will be performed 6 weeks (+/- 1 week) after surgery, before radiation.
10. Draw #7 will be performed 3 months (+/- 3 weeks) post-surgery.
11. Draw #8 will be performed 6 months (+/- 3 weeks) post-surgery.
12. Draw #9 will be performed 12 months (+/- 4 weeks) post-surgery.

12.1.1 LISTERIA SURVEILLANCE MONITORING BLOOD DRAW: Up to 45 ml of additional blood will be collected for safety follow up testing as *Listeria* surveillance monitoring. It will include CBC, CMP, including CRP and ESR and blood cultures for the detection of *Listeria*.

Patients in the control group will NOT undergo additional blood draw or monitoring. These blood draws will be performed at 3 months(+/- 2 weeks), 6 months(+/- 3 weeks), 9 months(+/- 1 Month), 12 months(+/- 1 Month), and every 4 months(+/- 1 Month) for year 2 and year 3 as mentioned in schedule above.

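### Section 10.8: Table A and the paragraph below it give inconsistent rules on whether dose 2 may follow persistent grade 2 or grade 3 toxicity

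*Combined protocol and SAP*

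**What the plan says.** Section 10.0 sets the exposure: "Two vaccinations with ADXS11-001 will be given". Section 12.1 places the second dose: "Draw #3 will be performed on the day of the second vaccination (day 15) before vaccine infusion". Section 10.8 rules out changes of dose but says that "treatment may be delayed or discontinued based on toxicities, as shown below in Table A".

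Table A covers one class of drug-related event: "Hematologic and non-hematologic, excluding cytokine release symptoms". Cytokine release symptoms have separate guidance in Table B (Section 10.10.1). The rows of Table A are:

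- Grades 1-2: "Continue therapy".
- Grade 3 that falls to grade 1 or lower, or to baseline, within 2 weeks of the last infusion: therapy restarts.
- Grade 3 that does not: "Discussion with study chair required".
- Grade 4: permanent discontinuation.

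The paragraph under the table addresses toxicity that has not come down to grade 0-1 in the 2 weeks after the last infusion. In that case "trial treatment should be discontinued after consultation with the Sponsor". It has one exception, which needs the agreement of Investigator and Sponsor: "subjects with a laboratory AE still at Grade 2 after 2 weeks may continue treatment in the trial only if asymptomatic and controlled".

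**The concern.** A site deciding on dose 2 has two rules on the same page and nothing that says which prevails. Section 10.8 points to Table A as the guide to delay and discontinuation, yet the paragraph adds a 2-week test that the grade 1-2 row lacks. It also omits the return-to-baseline alternative that the grade 3 rows contain.

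Two things are at stake. The first is safety: for the same event, one reading gives a further infusion and the other stops treatment. The second is exposure: the trial runs at several sites, and different readings would leave a mix of one-dose and two-dose patients that reflects local interpretation rather than the plan.

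**Working it through.** No sample size, power or error rate is involved, so the check is one of timing and then of text against text.

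**Timing.** Section 12.1 calls the day of the first dose Day 1 and puts the second on Day 15. The interval is 15 - 1 = 14 days = 2 weeks. The resolution window therefore closes on the day dose 2 is due. The Section 7.1 calendar schedules a CBC and CMP on Day 15, so a persisting laboratory event could come to light at that visit.

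**Grade by grade, at 2 weeks after dose 1.**

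| Status | Table A | Paragraph below | Result |
|---|---|---|---|
| Grade 1 | Continue | Criterion met | Consistent |
| (a) Grade 2 persisting, non-laboratory | Continue, no condition | Discontinue after Sponsor consultation | Direct conflict |
| (b) Grade 2 persisting, laboratory | Continue, no condition | Continue only with Investigator and Sponsor agreement, and only if without symptoms and under control | Conflict of conditions |
| Grade 3 resolved to grade 0-1 | Restart | Criterion met | Consistent |
| (c) Grade 3 back to a baseline above grade 1 | Restart | No baseline alternative; discontinue (a laboratory event at grade 2 could still meet the exception) | Conflict |
| (d) Grade 3 unresolved | Discuss with study chair, outcome open | Discontinuation after Sponsor consultation is the default | Different default and named party |
| Grade 4 | Permanent discontinuation | Criterion not met | Consistent, also with Section 13.0 |

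**Can case (c) occur?** Section 5 sets no limit on haemoglobin or blood counts at entry, so a baseline laboratory value above grade 1 is possible.

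**Does another section settle it?** No. Section 13.0 requires removal for toxicity only at grade 4 and is silent on grades 2 and 3. The paragraph refers the reader to a Section 4.6 on supportive care, but Section 4.0 concerns transoral surgery and supportive care is in Section 10.10.1.

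**Scale.** The rule governs 1 of 2 doses. Section 16.0 plans at most 22 vaccinated patients, 9 of them in stage 1, so each patient handled differently is 1/22 = 4.5% of the full cohort or 1/9 = 11.1% of the first stage. How many there would be is not computable: the documents give no rate of grade 2 or 3 toxicity still present at 2 weeks.

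**The case against.** The strongest reply is that the paragraph was meant only for grade 3 events that led to a hold. It repeats the 2-week test of the grade 3 rows, and its mention of an event still at grade 2 fits one that has fallen from grade 3. On that reading, ordinary grade 2 toxicity falls under the table alone, and (a) and (b) disappear for it. The reading is possible, but the paragraph speaks of toxicity without limiting the grade, so a site is not bound to adopt it. Even if adopted, it leaves (c) and (d).

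A second reply concerns scope, and it stands in part. Table A excludes cytokine release symptoms, which takes out fever, chills, nausea, vomiting, hypotension and others that Section 10.10.1 describes as lasting up to 24 hours. Fewer kinds of event can then fall in (a), the one grade 2 case where the actions are truly opposed. Table 1 does list related non-laboratory events outside that group, such as abdominal pain, constipation and back pain, but gives no time course.

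A third reply, on unresolved grade 3, also stands. A reader might infer that the instructions are opposite. They are not: both call for consultation, and stopping is one possible result of the table's discussion. The two named parties may even be the same, since Section 13.0 pairs sponsor with Study Chair and Section 17.0 can be read as making the chair the IND holder. Section 14.0, however, refers to a medical monitor of the sponsor, so this is not certain.

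Finally, a reader might try to size the problem from Table 1, where related grade 1-2 anaemia is (178 - 3)/290 = 60.3%. That figure does not do the job. It pools grades 1 and 2, covers several dose levels and repeated doses, and says nothing about persistence at Day 15. Anaemia is also a laboratory event, for which the paragraph can itself allow continuation.

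**Conclusion.** The inconsistency is real and stands in the current text. It is confined to four situations: persistent non-laboratory grade 2 (opposed actions), persistent laboratory grade 2 (unequal conditions), grade 3 back to a baseline above grade 1 (restart against discontinue, subject to the laboratory exception), and unresolved grade 3 (different default and named party).

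It would be too strong to say that eligibility for dose 2 is undefined in general, because the remaining grades are handled consistently and cytokine release symptoms are governed by Table B.

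Nor do the documents show that patients would be lost from the primary analysis. The pre-operative draw is tied to surgery, Section 13.0 asks for at least one vaccination, and Section 16.0 does not make two doses a condition of being counted. The statistical consequence is the number of doses behind a counted response, not whether the patient is counted.

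The conclusion rests on reading the paragraph as worded, without a grade limit, and on dose 2 being given on the scheduled day. The number of patients affected is unknown. The point merits correction because it bears on safety and on exposure to the second dose.

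**What to change.** Amend Section 10.8 so that Table A and the paragraph agree. Each combination of grade and resolution status at 2 weeks should have one instruction, one named decision-maker and one resolution criterion, with that criterion worded identically in both places. The amendment should also say whether the 2-week test applies to events that never exceeded grade 2, say whether the study chair and the Sponsor are the same party for this decision, and correct the reference to Section 4.6. Which rule and which threshold apply is for the sponsor and investigators to decide; no preference is expressed here.

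The cost is a wording amendment, with no added visits, samples or data.

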10.10 ADVERSE EVENTS AND SUPPORTIVE CARE: The most likely AEs associated with ADXS11-001 are comprised primarily of individual flu-like symptoms (e.g., fever, chills, body ache, and fatigue) or cytokine release symptoms (e.g., headache, nausea, vomiting, tachycardia, shortness of breath, hypotension and rash). The symptoms usually present within 2-4 hours after the completion of infusions and are often mild to moderate and transient in nature or responds quickly to symptomatic treatment. In rare instances they may last up to 24 hours. No cumulative toxicity has been observed.

Less likely AE's include increase heart rate, low blood pressure, muscle aches, headaches, allergic reaction, changes in blood chemistry, changes in blood counts, and short term changes in liver function.

Rare but serious AEs include high fever, difficulty breathing and hypotension.

Like all *Listeria*, ADXS11-001 has a tropism for the liver. Transient asymptomatic elevations of ALT and alkaline phosphatase were observed after dosing in the Phase 1 trial without prophylactic medication administration. For that reason, patients with significant liver disease are excluded, and particular attention is to be paid to hepatic abnormalities.

- 10.10.1 Supportive Care Guidelines: The major safety findings with ADXS11-001 occurring in $\geq 5\%$ of subjects, as of June 2016 (n=290) and being possibly, probably or definitely related include anemia (61.4%), chills (63.5%), fatigue (25.5%), fever (57.6%), nausea (36.9%), vomiting (30.3%), headaches (23.8%). Most are Grade 1-2 in severity. Subjects should receive appropriate supportive care measures as deemed necessary by the treating Investigator with consideration given to the criteria the items outlined below.

Nausea and vomiting- should be treated aggressively, and consideration should be given in subsequent cycles to the administration of prophylactic antiemetic therapy according to standard institutional practice. Subjects should be strongly encouraged to maintain liberal oral fluid intake.

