Cytokine Release Symptoms- are a constellation of inflammatory symptoms resulting from cytokine elevations associated with T cell engagement and proliferation. Symptoms related to cytokine release may include constitutional symptoms such as fever, chills, rigors, fatigue, headache, nausea, vomiting, rash, tachycardia, hypotension and shortness of breath which usually presents several hours after the infusion and lasts for up to 24 hours. These symptoms are caused by an increase in cytokines such as TNF α , IFN γ and IL-6, all of which have been shown to occur after ADXS11-001 administration, resulting from the body's immune response to the therapy. Although, symptoms are often Grade 1-2 and transient, resolving with symptomatic management within 30 minutes to 1 hour, in some instances (~6%) Grade 3-4 hypotension has been seen. Therefore, close monitoring of blood pressure is strongly recommended at baseline, and during the post-infusion period. Increased levels of IL-6 have been strongly associated with capillary leak which manifests as hypotension due to the cytokines involved. We have observed elevated IL-6 levels after infusion of ADXS11-001, with peak levels occurring 2-4 hours after infusion. Emerging evidence indicates that IL-6 antagonists, such as tocilizumab, have demonstrated good results in treating cytokine-induced hypotension [61, 62, 63, 64] and are therefore recommended for cases of severe hypotension refractory to supportive care (e.g., fluids and/or pressors).

The management of cytokine release symptoms and guidelines for subsequent treatment for subjects who have experienced these AEs are shown in the table below.

Table B Recommended Management Guidelines for Adverse Events Associated with Cytokine Release

Toxicity	NCI CTCAE Grade or Severity	Treatment	Modification for Subsequent infusions
Hypotension	1 Mild	
 Supportive care 	
 Increase pretreatment IV fluids (e.g., 500 ml -1L normal saline)
All other cytokine release symptoms (e.g. chills, rigors, fever, nausea, vomiting)	1	
 Supportive care 	
 No modification

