Hypotension	2 Moderate	
 Fluids and 1 dose of pressor (e.g. 0.3 mg epinephrine IM) Increase monitoring of vital signs If hypotension persist for more than one hour consider low dose corticosteroids (e.g. hydrocortisone 100 mg IV over 30 seconds) 	
 Extend infusion time to 2 hours. Increase pretreatment IV fluids (e.g. 500 ml -1L normal saline) Incorporate Glucocorticoid-Hydrocortisone or equivalent- 50 mg, IV, as premedication
All other cytokine release symptoms (e.g. chills, rigors, fever, nausea, vomiting)	2	
 Appropriate supportive care measure 	
 Extend infusion time to 2 hours. Consider increasing doses of prophylactic medications
Hypotension	3 Severe	
 Fluids, high dose pressors (e.g. Dopamine 10 µg/kg/min) +1 dose tocilizumab*(4mg/kg over 1 hour) If hypotension worsens or is unresponsive to above measures, administer corticosteroids 	
 Discuss with Sponsor

Toxicity	NCI CTCAE Grade or Severity	Treatment	Modification for Subsequent infusions
		
 If the subject's condition does not improve or stabilize within 24 hours of the tocilizumab dose, administration of a second dose of tocilizumab +/- corticosteroids should be considered. 	
All other cytokine release symptoms (e.g. chills, rigors, fever, nausea, vomiting)	3	
 Appropriate supportive care measures 	
 Extend infusion time to 2 hours. Consider increasing doses of prophylactic dose of NSAID, or antiemetic as appropriate
Hypotension/ Organ toxicity, mechanical ventilation	4 Life threatening	
 Vigilant supportive care Fluids High dose pressors, Tocilizumab (4mg/kg over 1 hour) +/- corticosteroids (hydrocortisone 100 mg IV infused over 30 seconds administered every 2 hours until symptoms resolve to <Grade 1) 	
 Permanently discontinue

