* Tocilizumab is a humanized, immunoglobulin G1k (IgG1k) anti-human IL-6R mAb approved for treatment of adult subjects with moderately to severely active rheumatoid arthritis (RA) who have had an inadequate response to Disease-Modifying Anti-Rheumatic Drugs (DMARDs), for the treatment of active polyarticular juvenile idiopathic arthritis (PJIA), and active systemic juvenile idiopathic arthritis (SJIA) in subjects 2 years of age and older. Tocilizumab works by preventing IL-6 binding to both cell-associated and soluble IL-6Rs. Although, it is not indicated for the treatment of cytokine release symptoms emerging clinical experience at several institutions has concluded that tocilizumab is an effective treatment for severe or life-threatening cytokine release symptoms. [61, 62, 63, 64]

Management of infusion reactions- While there is some overlap between the symptoms of cytokine release and infusion reactions, infusion reactions typically occur during the infusion, while symptoms associated with cytokine release typically occur after the infusion and are mediated by a different mechanism of action. Signs/symptoms of infusion reactions may include: allergic reaction/ hypersensitivity (including drug fever); arthralgia (joint pain); bronchospasm; cough; dizziness; dyspnea (shortness of breath); fatigue (asthenia, lethargy, malaise); headache; hypertension; hypotension; myalgia (muscle pain); nausea; pruritis/itching; rash/ desquamation; rigors/chills; sweating (diaphoresis); tachycardia; tumor pain (onset or exacerbation of tumor pain due to treatment); urticaria (hives, welts, wheals); vomiting.

Table C below shows the management guidelines for subjects who experience an infusion reaction associated with administration of ADXS11-001.

Table C: Management Guidelines for Infusion Reactions

NCI CTCAE Grade	Management

Grade 1 Mild reaction; infusion interruption not indicated; intervention not indicated
	
Increase monitoring of vital signs as medically indicated until the subject is deemed medically stable in the opinion of the Investigator.

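### Section 10.10.1 gives inconsistent conditions for tocilizumab: the text reserves it for severe hypotension that has not responded to supportive care, while Table B lists it with first-line measures at grades 3 and 4

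*Combined protocol and SAP*

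**What the plan says.** All the passages are in Section 10.10.1 (Supportive Care Guidelines).

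- **Text on cytokine release symptoms.** IL-6 antagonists, with tocilizumab as the example, "are therefore recommended for cases of severe hypotension refractory to supportive care (e.g., fluids and/or pressors". The next paragraph refers the reader to Table B for management.
- **Table B, hypotension grade 3 (severe).** The first bullet combines fluids, high dose pressors and "1 dose tocilizumab*(4mg/kg over 1 hour". The second bullet reads "If hypotension worsens or is unresponsive to above measures, administer corticosteroids". A second tocilizumab dose is to be considered "If the subject's condition does not improve or stabilize within 24 hours of the tocilizumab dose".
- **Table B, grade 4 (life threatening).** After vigilant supportive care and fluids, the row lists "High dose pressors, Tocilizumab (4mg/kg over 1 hour) +/- corticosteroids".
- **Footnote to Table B.** Emerging experience is said to show that "tocilizumab is an effective treatment for severe or life-threatening cytokine release symptoms".
- **Status of the guidance.** The section opens with "Subjects should receive appropriate supportive care measures as deemed necessary by the treating Investigator", and Table B is titled as recommended guidelines. Section 14.0 leaves the final decision on supportive therapy to the investigator and/or the patient's own physician.

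**The concern.** The text makes failure of supportive care the condition for tocilizumab. In the table, the first dose carries no such condition. A patient with grade 3 hypotension who recovers on fluids and/or a pressor is thus inside the table's rule and outside the text's rule.

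For a patient who does not recover, the text attaches tocilizumab to the failure. The grade 3 row attaches corticosteroids to it, tocilizumab having already been given.

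What is at stake is consistent handling of a serious, foreseeable toxicity. The trial has several sites, and two sites following the protocol in good faith could treat the same event differently. Nothing elsewhere settles it. Section 10.8 points to Appendix A for cytokine release guidance, but the Appendix A in the document covers drug ordering. The same section points to a Section 4.6 on supportive care, but Section 4.0 is about transoral surgery.

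**Working it through.** **1. The passages side by side**

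| Situation | Text | Table B | Footnote |
|---|---|---|---|
| Grade 1-2 hypotension | not covered | no tocilizumab | not covered |
| Severe hypotension, responds to fluids and/or pressors | no tocilizumab | one dose (grade 3); listed (grade 4) | within scope |
| Severe hypotension, refractory | tocilizumab | already listed; at grade 3, non-response leads to corticosteroids | within scope |
| Other grade 3 cytokine release symptoms | not covered | supportive care only | within scope |

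The second line is a direct conflict. The third is a difference in sequence. In the fourth, the footnote reaches further than either the text or the table, although it is worded as a statement about effectiveness and not as an instruction.

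The missing condition in the grade 3 row is hard to read as shorthand. The same row states non-response conditions explicitly for corticosteroids and for the second tocilizumab dose.

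**2. How often severe hypotension would arise**

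Inputs: grade 3-4 hypotension in 18 of 290 patients (Table 1, Section 2.3); up to 22 vaccinated patients (Section 16.0).

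- Rate: 18/290 = 6.2%, which agrees with the figure of about 6% in Section 10.10.1.
- Expected cases: 22 × 18/290 = 1.37.
- Chance of at least one: 1 − (1 − 18/290)^22 = 0.756, or 76%.
- Over the exact 95% confidence interval for 18/290 (3.7% to 9.6%): 0.8 to 2.1 expected cases, and a 57% to 89% chance of at least one.
- If the trial stops after the first 9 patients: 9 × 18/290 = 0.56 expected cases, and a 44% chance of at least one.

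**3. How often the passages would actually differ**

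The 76% counts every grade 3-4 case. The passages disagree about giving tocilizumab only when the case is not refractory. Let f be the refractory share. The documents do not give it, so the values below are assumptions.

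Chance of at least one such case in 22 = 1 − (1 − (18/290)(1 − f))^22

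| Assumed f | Rate of differing cases | Expected in 22 | Chance of at least one |
|---|---|---|---|
| 20% | 5.0% | 1.09 | 67% |
| 50% | 3.1% | 0.68 | 50% |
| 80% | 1.2% | 0.27 | 24% |

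**The case against.** **The passages can be read together.** The text says fluids and/or pressors, so failure of fluids alone could count as refractory. Table B escalates: grade 2 already has fluids and one pressor dose, and grade 3 moves to high dose pressors. A patient who needs those might be regarded as refractory already. This has force, because on that reading f is high and the gap is small. It does not close the gap. Table B assigns treatment by grade and does not require an earlier step to have failed, so a patient graded severe at onset meets all three measures at once.

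**The order relative to corticosteroids is partly inferred.** The text's sentence on tocilizumab does not mention corticosteroids. That is correct. The difference lies in what each passage attaches to non-response, and it is secondary to the conflict over the first dose.

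**The guidance is advisory.** This stands, and it means that neither reading is mandatory. Advice to several sites should still not give two answers.

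**A stronger reading that the documents do not support.** A reader might infer that uneven tocilizumab use biases the T-cell endpoint, and that patients given tocilizumab or corticosteroids should be scored as non-responders in a sensitivity analysis. The footnote says that "Tocilizumab works by preventing IL-6 binding to both cell-associated and soluble IL-6Rs", but nothing in the documents says that a dose changes the E6/E7 response, in either direction. Nor does the pre-operative sample alone decide response, since Section 16.0(c) also counts responses at 3 and 6 weeks after surgery.

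The suggested analysis would also capture corticosteroid use unrelated to this conflict. Table B includes hydrocortisone as premedication after grade 2 hypotension, where the passages do not disagree. Table 1 has 58 − 18 = 40 hypotension cases below grade 3, or 22 × 40/290 = 3.0 expected here (the grade 2 share is not given), against 1.4 at grades 3-4.

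**Conclusion.** Wrong as written: an internal contradiction in a safety rule. The text, the grade 3 and grade 4 rows of Table B, and the footnote do not state the same condition for tocilizumab. The conflict is confined to severe or life-threatening hypotension that is not refractory, together with the sequence relative to corticosteroids when it is.

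The number of patients affected is small, but the situation may well occur: the chance of at least one case where the passages differ is 24% to 67% for an assumed refractory share of 80% down to 20%. This assumes that the Table 1 rate carries over. That rate pools grades 3 and 4 and doses from 5×10^7 to 1×10^10 CFU, whereas this trial uses 1×10^9. It also assumes that 22 patients are vaccinated. An effect on the immune endpoint is not shown and forms no part of the conclusion.

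**What to change.** Reconcile four places in Section 10.10.1: the text on cytokine release symptoms, the grade 3 row of Table B, the grade 4 row, and the footnote. One condition for tocilizumab, and one order relative to corticosteroids, should appear in all of them. Which condition and order to adopt is for the sponsor and clinical investigators to decide.

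The cost is a wording change to the protocol. It needs no new data, no change to sample size and no change to the analysis in Section 16.0.
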